3.0 Study Synopsis

Sponsor/ Investigator Sponsored Study	[name].
Study Title:	Senolytic Drugs Attenuate Osteoarthritis-Related Articular Cartilage Degeneration: A Clinical Trial
Protocol Number:	2019-16
Study Design:	Randomized, double-blind, placebo controlled
Study Duration:	Approximately 36 months Enrollment 18 months Follow-up 18 months
Randomization:	Subjects are to be assigned to one of two treatment groups using a 1:1 (Fisetin/placebo) randomization scheme.
Study Arms/Medication	Active Treatment: Fisetin 100 mg capsules (~20 mg/ kg/ day) will be administered orally for two consecutive days (days 1 and 2) followed by 28 days off. A second course will be given for two consecutive days (days 31 and 32) Placebo Control: Appearance matched capsule p.o. dose to match the number of capsules as if subjects were receiving active treatment. Placebo capsules will be administered orally for two consecutive days (days 1 and 2) followed by 28 days off. A second course will be given for two consecutive days (days 31 and 32)
Blinding Procedure:	The block randomization chart will be securely kept by an Unblinded Study Team member and at the Vail Hospital Pharmacy (point of subject distribution). All study subjects and other Study Team members including the Principal Investigator will be blinded to treatment through 18 months follow-up. In addition, any individuals engaged by the Principal Investigator to provide and/or document assessment of study endpoints will be blinded to treatment.
Sample Size and Study Population:	A total of 100 male or female subjects 40-80 years of age will be recruited from a single clinical site, where the Principal Investigator conducts patient care.
Objectives:	Primary Objective

	
To evaluate as compared to placebo:
 
The safety of administering Fisetin in subjects with osteoarthritis (OA) of the knee.
 
Secondary Objectives
 
To evaluate as compared to placebo:
 
 1. Reduction of pro-inflammatory and cartilage degenerating SASP markers; 2. Improvement in physical function of the Study Knee; 3. Improvement in patient reported outcomes; 4. Improvement in the quality of articular cartilage in the Study Knee with quantitative magnetic resonance imaging (MRI); 5. Reduction in time to conversion to alternative treatment.

Endpoints:
	
Primary Endpoint:
 
Occurrence of adverse events.
 
Secondary Endpoints
 
Statistically significant as compared to placebo:
 
 1. Improvement in serum measures of inflammation and cartilage degenerating senescence associated secretory phenotype (SASP) markers; 2. Improvement in lower-extremity kinematic testing with video-motion analysis; isokinetic dynamometry testing, functional performance testing, range of motion (ROM);

	
 3. Improvement in patient reported outcomes (PROs), including: IKDC, Lysholm, TEGNER, WOMAC and SF-12 surveys; 4. Improvement in the quality of articular cartilage in the knee joint as measured by T2 and T1rho relaxometry; 5. Days from day one of Study Medication intake to conversion to alternative therapy. 
Additionally, we will review and discuss any possible correlation among secondary endpoint results.

Inclusion Criteria	
Subjects will be included if all the following criteria are met:
 
 1. Are male or female, ages 40-80; 2. Are willing to comply with all study related procedures and assessments; 3. Are ambulatory as defined by ability to complete functional performance testing; 4. Radiographic evidence of Kellgren-Lawrence grade II-IV osteoarthritis in one or both knees; 5. Scores 4-10 on the Numerical Rating Scale (NRS) for pain; 6. Stable dose of screening/baseline medications for at least 2 months prior to the anticipated date of study drug dosing.
Exclusion Criteria:	
Subjects will be excluded if any of the following criteria are met:
 
 1. Females who are nursing, pregnant or planning to become pregnant during the duration of study drug dosing; 2. Males who do not wish to abstain from sex or use contraceptive protection during study drug dosing and for 2 weeks after the last dose; 3. Subjects who do not have the capacity to consent themselves; 4. Subjects who are unable to tolerate oral medication; 5. Subjects having previously undergone any of the following treatments in the stated time window: 
 -Surgery on the Study Knee in the past 6 months;

	
 -Partial or complete joint replacement in the study knee. Partial or complete joint replacement in the contralateral knee is acceptable as long as the surgery was performed at least 6 months prior to enrollment and the operative knee is asymptomatic; -Patients who have undergone arthroscopic surgery (including microfracture and meniscectomy) on the StudyKnee in the last 2 years prior to the Screening visit or are anticipated to have arthroscopic surgery on either knee at any time during the study period; -Steroid injection, including extended-release corticosteroid (e.g., Zilretta®) within the last 5 months; -Biologic (platelet-rich plasma, bone marrow, adipose tissue/cells) or hyaluronic acid injection into the Study Knee in the past 6 months; 
6. Subjects with any of the following drug/medication statuses:
 
 - Currently taking Losartan; -Currently taking Warfarin or related anticoagulants; - Opioid analgesics taken in the past 8 weeks and are not willing to discontinue these medications through the duration of the study; - Senolytic agents taken within the past 6 months and are not willing to discontinue these medications through the duration of the study, including: Fisetin, Quercetin, Luteolin, Dasatinib, Piperlongumine, or Navitoclax; -Drugs that induce significant cellular stress and are not willing to discontinue these medications through the duration of the study, including alkylating agents, anthracyclines, platins, other chemotherapy drugs; 
- Subjects taking the following other drugs if they cannot be held (per the Principal Investigator) for at least 2 days before and during administration of Fisetin: cyclosporine, tacrolimus, repaglinide, and bosentan ;
 
7. Subjects with any of the following disease statuses:

--	---

	
 -Significant liver disease (i.e. greater than or equal to 2x the upper limit of normal bilirubin levels) or as in the opinion of the Principal Investigator; -Significant renal disease (eGFR of <60 ml/min/1.73m²) or as in the opinion of the Principal Investigator; -History of other formally diagnosed joint diseases including, osteonecrosis, acromegaly, Paget's disease, Ehlers-Danlos Syndrome, Gaucher's disease, Cushing's syndrome, Stickler's syndrome, joint infection, hemophilia, hemochromatosis, or neuropathic arthropathy of any cause; -Any active systemic autoimmune disease with musculoskeletal involvement or any history of systemic inflammatory arthritis; -Patients with type 1 or 2 diabetes (HbA1c \geq 6.5%) and/or taking medications that affect insulin levels, including: Metformin (within the last week), Glucocorticoids (within the last month), Acarbose (within the last week); 
8. Subjects unable to safely practically undergo an MRI (BMI > 40 kg/m²) or size exceeding limits of MRI equipment, implanted metal in study knee near joint surface, incompatible implant/device, severe claustrophobia;
 
9. Subjects that have any medical condition, including laboratory findings and findings in the medical history or in the pre-study assessments, that in the opinion of the Investigator constitutes a risk or contraindication for participation in the study or that could interfere with the study objectives, conduct or evaluation or prevent the patient from fully participating in all aspects of the study.

Screening	
Visit 1 (Screening/Enrollment)
 
At the first patient visit, the following procedures will be performed:
 
 1. Full explanation of the clinical study, execution of Informed Consent, copy of signed informed consent sent home with research subject; 2. Subject will be assigned a de-identified study number;

	
 3. Vital signs; 4. Medical and surgical history; 5. Demographic information; 6. Details of injury; 7. Severity of injury; 8. Medications; 9. Physical exam with range of motion (ROM) of the target limb; 10. BMI; 11. Urine pregnancy test for Women of Child Bearing Potential (WOCBP); 12. Blood analysis; 13. Completion of augmented PROs, including: NRS, IKDC, Lysholm, TEGNER, WOMAC and SF-12; 14. A radiograph of the target knee will be performed to confirm the presence of Kellgren-Lawrence grade II-IV OA; 15. The patients' medical record will be reviewed, and the subject will be interviewed to determine if inclusion/exclusion criteria are met; 16. Randomization. 
Patients who have met all eligibility criteria will be assigned, 1:1 via block randomization, to one of the two blinded study groups.
 
Visit 2 (Baseline) (Within 3 months of Visit 1)
 
Some procedures performed in this visit may be performed in Visit 1 provided that Informed Consent has been signed.
 
 1. Urine pregnancy test for Women of Child Bearing Potential (WOCBP) 2. Quantitative MRI; 3. Kinematic movement; 4. Assessment of muscle strength, isokinetic dynamometry; 5. Functional performance testing.
--	---

	
After randomization is performed, a Study Team member will then inform the Vail Hospital pharmacist of the subject's assigned randomization code the study medication will be obtained. The subject will take the first dose of study medication at the clinic.
 
Subjects will be instructed to self-medicate for day 2 followed by 28 days off. They will be instructed to begin a second course of treatment for two consecutive days (days 31 and 32).
 
Subjects will be reminded at Visit 3 in-person and over the phone 2-4 days prior to the last dosing of study medication about their upcoming dosing. If applicable, they will also be reminded to withhold current medications as instructed by the PI.
 
A Medication Log recording medication administration will be provided to the subject with instructions to complete during the period of administration.

Subject Follow-up:	
All adverse events and protocol deviations will be assessed at each follow-up visit.
 
Visit 3: Two Weeks after first dose of Fisetin or Placebo (+/- 2 days) All subjects will return to the study site 2-weeks from the subject's last dose of Fisetin or placebo. The following procedures will be performed:
 
 1. Blood Analysis 
Visit 4: Two Weeks from the Subject's Last Dose of Fisetin or Placebo (+/- 10 days) All subjects will return to the study site 2-weeks from the subject's last dose of Fisetin or placebo. The following procedures will be performed:
 
 1. Vital signs; 2. Medical and surgical history; 3. Physical exam with ROM of target limb; 4. Blood analysis;

	
 5. Medications; 6. Completion of augmented PROs, including: NRS, IKDC, Lysholm, TEGNER, WOMAC and SF-12; 7. Protocol deviation assessment; 8. Adverse event assessment. 
Visit 5: Six Months from the Subject's First Dose of Fisetin or Placebo (+/- 4 weeks)
 
 1. Vital signs; 2. Medical and surgical history; 3. Physical exam with ROM of target limb(s); 4. Blood analysis; 5. Completion of augmented PROs, including: NRS, IKDC, Lysholm, TEGNER, WOMAC and SF-12; 6. Medication; 7. Protocol deviation assessment; 8. Adverse event assessment; 9. Quantitative MRI; 10. Lower-extremity kinematic testing with video-motion analysis; 11. Isokinetic dynamometry testing; 12. Functional performance testing. 
Visit 6: 12 Months following First Dose of Study Medication (+/- 4 weeks) All procedures performed in Visit 5 will be repeated.
 
Additional Remote Follow-up In addition to the in-clinic follow-up visits above, the following remote follow-up will be conducted:

--	---

	
 • Once Every 3 days During FIRST 6 weeks of Study Medication Treatment then Once a Week for an ADDITIONAL 6 weeks Subjects will complete an augmented NRS questionnaire. • At 18-Months After First Dose of Study Medication (+/- 4 weeks) Subjects will complete the augmented PROs electronically, including: NRS, IKDC, Lysholm, TEGNER, WOMAC and SF-12. • Phone Calls Subjects will be contacted by phone three times while they are taking study medication to remind them to take the next dose of drug and to capture any adverse events.
Statistical Methods	Please refer to Section 15.0 of this document

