5.0 Introduction

5.1 Background and Significance

The Steadman Clinic (TSC) and the Steadman Philippon Research Institute (SPRI) are proposing a Phase 1-2 prospective clinical study to collect safety and efficacy data on the use of Fisetin (FIS), which is a nutritional supplement and senolytic agent, in treating patients with Osteoarthritis (OA) of the knee. This study is entitled: *Senolytic Drugs Attenuate Osteoarthritis-Related Articular Cartilage Degeneration: A Clinical Trial*.

Recently, several senolytic compounds that selectively kill senescent cells in vitro and in vivo without affecting quiescent or proliferating cells were identified¹. These senolytic drugs target and inhibit anti-apoptotic pathways that are upregulated in senescent cells, thereby inducing apoptotic cell death and abrogating systemic Senescence-Associated Secretory Phenotype (SASP) factors.

As further discussed in 5.3 of this protocol, we have demonstrated in pre-clinical studies that treatment with senolytic drugs including (FIS, Dasatinib (D), Quercetin (Q) and Alvespimycin) can reduce the incidence/severity of many age-related disorders, including OA in naturally aged and progeroid mice (accelerated aging). These studies have shown that senolytic treatment (D/Q and FIS) can delay articular cartilage degeneration in a murine model of natural and accelerated (progeria) aging.

Based on this promising pre-clinical data, we believe it may be possible to delay or even reverse joint degeneration, damage to ligaments, menisci, cartilage, thereby resulting in the extension of high-level function and preservation of quality of life.

In this randomized, double-blind, placebo-controlled clinical trial, we intend to measure and compare safety via the gathering of all adverse events and preliminary evidence of efficacy through recording of SASP, inflammatory biomarkers and senescent cells. In addition, magnetic resonance imaging (MRI) exams, self-reported outcomes, functional performance and other relevant clinical data will be gathered. Possible correlation among outcomes, both structural and non-structural, will be described.

Each subject is to be followed for 18 months.

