7.4 Administration of Study Medication

7.4.1 Route and Dosage

Fisetin (FIS) 100 mg capsules (~20 mg/ kg/ day) will be administered orally for two consecutive days (days 1 and 2) followed by 28 days off. A second course will be given for two consecutive days (days 31 and 32)

Placebo (visually identical) will be taken orally using the same dosing schedule described for FIS. Number of capsules per day will be the same number as if receiving FIS.

There are no recommended dosing adjustments for kidney or liver dysfunction.

Subjects will be instructed to complete dosing in as short of a time as possible, with a goal of 10 minutes and a maximum time of 60 minutes to complete ingestion of the capsules. They will further be instructed not to increase medication dosing should a particular dose be missed.

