7.5.2 Study Duration

When every treated subject has reached 18 months following treatment, the study will be considered complete, and the data will be summarized. It is estimated that enrollment will take approximately 18 months. Each study subject will be followed for 12 months, which will be considered the final visit. The PROs will be administered electronically at 18 months. The total duration of Study is approximately 36 months. An additional 4 months will be spent closing the study database and in data analysis.

The proposed start date is December 1, 2019, with anticipated last visit September 1, 2022.

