12.2 Recording Adverse Events

Adverse events that occur during Study Medication administration will be recorded. Terms should be recorded consistently, using acceptable medical terms. When possible, a diagnosis should be identified as the AE (i.e., disease or syndrome) rather than the component signs and symptoms, and recorded on the case report form (e.g., record congestive heart failure rather than dyspnea, rales and cyanosis). However, signs and symptoms considered unrelated to encountered syndromes or diseases are to be recorded as individual AEs (e.g., if congestive heart failure and severe headaches are observed at the same time, each experience is to be recorded as an individual AE). The AE should not be recorded as a procedure or clinical measurement (i.e., a laboratory or vital sign) but should reflect the reason for the procedure or diagnosis.

Death is considered to be an outcome of an AE. The cause of death (rather than the term “death”) should be recorded on the serious AE and death report case report forms.

Subjects should be encouraged to report AEs spontaneously or in response to general, non-directed questioning. At each required visit (or whenever reported) during the study, all AEs that have occurred since the previous visit must be recorded on the AE case report form.

All AEs, regardless of seriousness, severity, or presumed relationship to the treatment must be recorded using medical terminology.

All AEs must be followed until resolution or until a stable clinical endpoint is reached. All measures required for AE management and the ultimate outcome of the AE must be recorded in the study document. All adverse events that occur in the study population will be tabulated and summarized.

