If the event is felt by the Principal Investigator to be either a SADR or an adverse reaction, every effort will be made to identify the event as related to the Study Medication. Adverse events that are generally felt to be attributable to the Study Medication occur in close temporal relationship to the onset of dosing. A discussion of AEs that are common with the Study Medication is found in the **Section 13.0** of this document.

All adverse reactions and SADRs will be followed until resolution or the Investigator judges the experience to be chronic or stable.

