15.5 Endpoints

15.5.1 Primary Endpoint

The safety of FIS administration is the primary endpoint of this study. All adverse events will be compared by category of description incidence, relatedness to treatment, severity, duration and expectedness. The occurrence of non-serious and serious and unexpected adverse events will be compared between treatment groups. Bivariate analysis will be performed between group and each safety variable of interest independently. When comparing the two treatment groups, dichotomous (yes/no) endpoints will be assessed for association using Fisher's exact test. Adverse events and symptoms that may occur multiple times in a single subject will be analyzed as count variables, and group differences will be assessed using simple Poisson regression or simple negative binomial regression.

This is a small Phase I/II trial in which to assess safety, thus we will report all safety data thoroughly and aim to liberally identify potential side-effects and risks that may warrant close study in future, larger trials. No adjustments will be made for multiple comparisons in this set of safety endpoints.

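### Section 15.5.1 sets no onset window for adverse events, so its pooled comparisons dilute any reaction close to the four dosing days

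*Combined protocol and SAP*

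**What the plan says.** The Synopsis and Section 8.2.1 state the primary endpoint in a few words, "Occurrence of adverse events", with no time frame. Section 15.5.1 makes it operational. It states that "The occurrence of non-serious and serious and unexpected adverse events will be compared between treatment groups", and it also plans comparisons by category, relatedness, severity, duration and expectedness. Yes/no variables go to Fisher's exact test and repeat events to Poisson or negative binomial regression. There is no multiplicity adjustment, and the declared aim is to be liberal in picking up possible side effects. None of these comparisons is restricted by date of onset.

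On exposure, Section 7.4.1 says study medication "will be administered orally for two consecutive days (days 1 and 2) followed by 28 days off", with a second course on days 31 and 32. That makes four dosing days.

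On follow-up, the Synopsis says "All adverse events and protocol deviations will be assessed at each follow-up visit". The Appendix B schedule marks AE review at Visits 3 to 6, the phone calls and unscheduled visits. It has no AE mark at the 18-month questionnaire. Section 7.5.2 says "Each study subject will be followed for 12 months, which will be considered the final visit", while Section 5.1 says "Each subject is to be followed for 18 months".

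On timing, Section 12.2.3 says "Adverse events that are generally felt to be attributable to the Study Medication occur in close temporal relationship to the onset of dosing". Section 12.2.1 already defines an onset date for each event.

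On what is recorded, Section 12.2 opens with "Adverse events that occur during Study Medication administration will be recorded". The same section then requires every AE since the last visit to be recorded at each required visit during the study.

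**The concern.** An acute reaction to a drug taken on four days would appear in a short stretch of a year-long record. The rest of the record adds background events at the same rate in both arms. Section 12.1 makes that background larger: it expects knee symptoms to fluctuate throughout follow-up, and it counts symptoms that become longer, more frequent or more intense as AEs.

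As background accumulates, the proportion with any AE approaches its ceiling in both arms and the ratio of event counts is pulled towards 1. A sizeable reaction near dosing could then give an unremarkable pooled result. That works against the liberal aim of Section 15.5.1. It could also be misread as support for the Section 15.1 hypothesis that fisetin does not raise the AE rate, for which no margin is set.

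**Working it through.** **The plan's own figure.** Section 15.6 sizes the trial on T1rho, not on safety. With SMD 0.73, two-sided 0.05 and 80% power, n = 2 × (1.960 + 0.842)² / 0.73² = 2 × 7.85 / 0.533 = 29.5, so 30 per group, as stated. Adding 6 gives 36 per group. The cap of 100 allows 50 per group. No power is stated for the primary safety endpoint, so both sizes are used here.

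**Window.** The last dose is on day 32. Visit 4 is targeted two weeks later, on day 46. 46 / 365 = 12.6%, so about 87% of a 12-month record lies after that day.

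**Assumptions, none given in the documents.** Background is λ = 1, 2 or 4 AEs per subject-year in both arms. Reaction risk is r = 33% on fisetin, always with onset inside the window, which follows the Section 12.2.3 premise.

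**Any AE.** Placebo risk is p0 = 1 − exp(−λT). Fisetin risk is p1 = 1 − (1 − p0)(1 − r). T is 1 year or 46/365 year. Power is the exact two-sided Fisher test at 0.05, by enumeration. Worked case for λ = 2: over 12 months p0 = 1 − exp(−2) = 86.5% and p1 = 1 − 0.135 × 0.67 = 90.9%. In the window p0 = 1 − exp(−0.252) = 22.3% and p1 = 1 − 0.777 × 0.67 = 47.9%.

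| λ per year | 12 months: p0 vs p1 | Power, 36 / 50 per arm | Days 1-46: p0 vs p1 | Power, 36 / 50 per arm |
|---|---|---|---|---|
| 1 | 63.2% vs 75.4% | 14% / 20% | 11.8% vs 40.9% | 75% / 90% |
| 2 | 86.5% vs 90.9% | 4% / 5% | 22.3% vs 47.9% | 54% / 71% |
| 4 | 98.2% vs 98.8% | <1% / <1% | 39.6% vs 59.5% | 29% / 46% |

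At a lower background of 0.5 per year and 36 per arm, power is 29% over 12 months and 88% in the window.

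**Counts.** Here fisetin is assumed to add 0.5 events per subject, with background frailty variance 0.5 and 36 per arm. At λ = 2 the rate ratio is (2 + 0.5) / 2 = 1.25 over 12 months and (0.252 + 0.5) / 0.252 = 2.98 in the window. Simulated power for λ = 1, 2, 4 is about 36%, 19% and 10% over 12 months, and about 92%, 82% and 61% in the window (simulation error about one percentage point).

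**One AE category.** The same Fisher formula is used with r = 33%, 36 per arm and a low category background:

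| Category background per year | 12 months | Days 1-46 |
|---|---|---|
| 0.05 | 91% | 98% |
| 0.10 | 80% | 97% |
| 0.25 | 54% | 94% |

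**A smaller reaction.** With r = 10%, 36 per arm and λ = 1, 2, 4, any-AE power is 4%, 2% and <1% over 12 months, and 11%, 7% and 5% in the window.

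**The case against.** The strongest reply is that Section 15.5.1 never names a pooled any-AE test as its headline. It plans a family of unadjusted comparisons, each made separately. A common, distinctive reaction, such as one of the gastrointestinal effects listed in Section 13.1, should appear in its own category: 91% or 80% power over the full 12 months at category backgrounds of 0.05 or 0.10 per year. Relatedness is also a partial time filter, because the Section 12.2.3 categories refer to whether exposure and event are reasonably related in time, and the Principal Investigator judges this while blinded. This stands. A reader might infer that the trial has almost no power to show a fisetin reaction, but the documents do not support that for the full set of planned comparisons.

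A second reply is that the inputs favour the window. The background and reaction rates are assumed, and the model places every reaction inside the window, so part of the contrast is built in. This also stands, and it is why the figures are shown as ranges. The contrast has the same direction at 36 and 50 per arm.

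A third reply is that the whole follow-up is a sensible frame for early safety work, since Section 13.1 reports positive Ames and micronucleus findings. That is a good reason not to let a window replace the long comparison. It is no argument against reporting both.

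What these replies do not answer is that relatedness is a judgement rather than a fixed rule, that no comparison uses the onset dates, and that category comparisons also improve with a window.

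**Conclusion.** The point holds in a limited form. The pooled any-AE and count comparisons are diluted by follow-up long after dosing. Under the stated assumptions at 36 per arm, a 33% reaction has any-AE power of 14% or less over 12 months at 1 to 4 background AEs per year, against 29% to 75% for days 1-46. Category comparisons are less affected, and the gain there depends on how common the complaint is.

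A window does not cure small numbers: at 36 per arm a 10% reaction is unlikely to be detected on either basis.

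Two stronger inferences should be avoided. The documents do not make the pooled test the main analysis. Nor do they clearly set the AE record at more than 12 months: Appendix B schedules no AE review at 18 months, and Section 12.2 contradicts itself on when AEs are recorded. The visit schedule favours the reading to month 12, but the text needs to settle it. This is an inexpensive improvement that should be made, not a fatal flaw.

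**What to change.** In the Synopsis, Section 8.2.1 and Section 15.5.1, prespecify the any-AE, count and by-category comparisons for AEs with onset from first dose through a fixed day, the same in both arms. Day 46, the Visit 4 target, is one candidate. Define membership by the onset date under Section 12.2.1 and not by the visit at which the event was reported, because Visit 4 may fall 10 days either side of its target.

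Report these alongside the same comparisons over the whole follow-up, with equal prominence, so that late events remain visible.

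Reconcile the two statements in Section 12.2 on whether AEs are recorded only during study medication administration or at every visit during the study, and state the end of the AE recording period.

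The cost is wording only, with no new data or visits. The downside is one more set of unadjusted safety comparisons, and so some additional chance findings, which is consistent with the liberal screening aim of Section 15.5.1.
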